12 HEALTH OUTCOMES ANALYSES

Health outcome analysis is not applicable to this study.

13 INTERIM ANALYSIS

Interim analysis is not applicable to this study.

14 DETERMINATION OF SAMPLE SIZE

A sample size of 48 subjects will provide 90% power to detect whether change from baseline to end-of-study visit in the FACE-Q Satisfaction with Facial Appearance Overall Scale Rasch-transformed score is different from zero, assuming a mean change of 12.0 and a standard deviation of 20.0. This calculation is based on a 1-sample, 2-sided t-test at 5% significance level. The assumptions of mean and standard deviation are based on FACE-Q results from Allergan HARMONY Study GMA-CMB-14-001. With a 20% drop-out rate (for early withdrawals and/or subjects who failed to duly complete the FACE-Q Satisfaction with Facial Appearance Overall Scale assessment at end of study), 60 subjects will be enrolled. From the 60 subjects planned to enroll in this study, approximately 20 subjects will be treated with BELKYRA.

Subjects will be assigned to study treatment only if they meet the inclusion criteria and none of the exclusion criteria. Subjects who discontinue treatment will not be replaced.

EXACT software (version 6) was used to confirm the sample size in the protocol.

15 STATISTICAL SOFTWARE

Statistical analyses will be performed using [REDACTED]

16 DATA HANDLING CONVENTIONS

16.1 Visit Time Windows

All subjects will sign an informed consent form (ICF), and begin the study at the screening visit (V0).

Subjects receiving BELKYRA treatment will enter the study at V1 and continuing through V12. There will be no less than 1 month between repeat BELKYRA treatments and the final BELKYRA treatment. Subjects not receiving BELKYRA following screening (V0) will enter the study at V7 to begin treatment with fillers, SkinMedica, and BOTOX Cosmetic as indicated in the study design diagram above.

16.2 Handling of dropouts missing data

After the subjects exit the study, the values for missed future visits will not be imputed. For subjects who discontinued from the study, the efficacy data collected on the exit visit will be mapped to scheduled visit.

16.2.1 Handling of missing or incomplete dates

Missing or incomplete dates will not to be imputed. There are cases where dates are missing for which visits and results are also missing, imputation will only be done on visits and results, but not on dates.

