6.2 Evaluable Population

Evaluable population is defined as all subjects as defined in the Full Analysis Population who have had at least one post-treatment efficacy assessment at the final visit (V12).

The Full Analysis Population will be used for subject disposition, demographics and baseline characteristics summary will be used for safety analyses. The Evaluable Population will be used on demographics and key efficacy endpoints as well.

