10 EFFICACY ANALYSES

The primary efficacy endpoint is the change from baseline to the final visit in the overall Rasch-transformed scores of the FACE-Q™ Satisfaction with Facial Appearance Scale. The scale data will be analyzed by using paired t-test. If normality is unmet, Wilcoxon signed-rank test is used to replace paired t-test. If skewness of FACE-Q change from baseline is not close to zero, the change data of FACE-Q is not considered as normally distributed. In this case, one-way nonparametric procedure with Wilcoxon option will be used to replace paired t-test.

One-sample paired t-test is performed on changes at end of study. The following statistics will be provided;

Label of Statistics	Description
N	Number of subjects of overall or a subgroup
Mean	Mean change of FACE-Q™ Scale
SD	Standard deviation of Mean Change
SEM	Standard error of Mean Change
Median	Median of Changes
Minimum, Maximum	Minimum, Maximum (of Changes)
Pr > t	p value of Mean Change through paired t-test, or that of Wilcoxon signed-rank test
95% CIs	95% Confidence Intervals of the Mean, lower and upper limits

The efficacy analyses will be based on the Evaluable population. Baseline for efficacy is defined as the last nonmissing assessment before the first dose of study treatment. All statistical tests will be 2-sided hypothesis tests performed at the 5% level of significance for main effects. All confidence intervals will be 2-sided 95% confidence intervals, unless stated otherwise.

Hypothesis testing will be performed at a 0.05 significance level (2-sided). Since BELKYRA and without BELKYRA are the major treatment cohorts, unless specified, all endpoints will be summarized by those two groups (BELKYRA and without BELKYRA) and overall respectively. However, this study is not designed to compare the efficacy and safety outcomes between subjects treated with BELKYRA and those treated without BELKYRA. All discussion and interpretation related to study outcomes will be mainly focused on the overall results.

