10.3.2.1 Global Aesthetic Improvement Scale (GAIS)

There are two assessment categories in GAIS at V12; Subject rating and Investigator rating. Descriptive statistics in frequency and percentage of scales at end of the study, in the 5-point scale from -2 to +2 are provided for both of assessments by investigators and subjects, and by subgroups as well.

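### Does the SAP's clause on imputing missing visits and results (16.2.1) conflict with its no-imputation rule (16.2) in a way that changes the primary FACE-Q result?

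*SAP*

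**What the plan says.** Protocol 11.4.3 leaves the missing-data strategy to the SAP. The SAP then has two relevant sentences.

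- SAP 16.2, on subjects who leave: "After the subjects exit the study, the values for missed future visits will not be imputed". It adds that for those who discontinue "the efficacy data collected on the exit visit will be mapped to scheduled visit".
- SAP 16.2.1, headed as being about missing or incomplete dates, first says that dates are not imputed and then: "There are cases where dates are missing for which visits and results are also missing, imputation will only be done on visits and results". No method, variable or visit is named.

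Three other places decide which subjects these sentences can touch.

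- SAP 10 bases efficacy on the Evaluable Population and says: "One-sample paired t-test is performed on changes at end of study". Its results table describes N as "Number of subjects of overall or a subgroup".
- SAP 6.2 defines Evaluable subjects as those in the Full Analysis Population "who have had at least one post-treatment efficacy assessment at the final visit (V12".
- SAP 14 allows 20% loss, and counts in that loss "subjects who failed to duly complete the FACE-Q Satisfaction with Facial Appearance Overall Scale assessment at end of study".

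**The concern.** In the visible text the only post-baseline time point for the primary score is the final visit. A case where date, visit and result are all missing would then be a missed final visit. For a subject who has left, SAP 16.2 says not to impute that visit, while 16.2.1 read alone says its result will be imputed. The only other imputation rules visible in the SAP are for adverse-event severity and relationship, so an analyst who took 16.2.1 at its word would have to invent a method, in an open-label single-arm study whose primary aim is to quantify a change.

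A second group also seemed exposed. SAP 10.3.2.1 says: "There are two assessment categories in GAIS at V12; Subject rating and Investigator rating". One investigator rating at V12 is therefore enough to make a subject Evaluable even if the FACE-Q is blank, and 16.2 does not mention that case. Because N is described as a count of subjects, the results table might not show whether such scores had been filled in.

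At stake would be the size and precision of the reported change. Under the planned effect, its significance would not be in doubt.

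**Working it through.** **Step 1. Which subjects could the two rules both reach?** The clause in 16.2.1 applies only when date, visit and result are all missing.

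| Subject | Does the 16.2.1 condition hold? | Evaluable (SAP 6.2)? | In the primary test? |
|---|---|---|---|
| Leaves early, no exit assessment | Yes | No: no V12 efficacy assessment | No |
| Leaves early, FACE-Q done at exit | No: a result exists | Yes, with exit data taken as V12 | Yes, observed score |
| Stays in, but V12 and any replacement visit missed | Yes | No | No |
| Attends V12, FACE-Q blank, GAIS rated | No: the visit took place | Yes | No: no change score |
| Attends V12, FACE-Q done, date not recorded | No: visit and result exist | Yes | Yes, observed score |

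The second row takes the unnamed scheduled visit in 16.2 to be V12. Protocol 11.1 supports this, since it asks subjects who discontinue to return for end-of-study data collection. So does the protocol's contents entry for 6.2.3.4, which treats V12 as the final or early-termination visit.

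In no row does a subject both meet the condition in 16.2.1 and belong to the Evaluable Population. The same holds for the other FACE-Q scales, which SAP 10.3 analyses in the same way and population.

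**Step 2. The plan's figures.** SAP 14 gives 48 subjects, mean change 12.0, SD 20.0 and 20% loss. The loss allowance reproduces: 48 / (1 − 0.20) = 60 enrolled, so 12 missing. The 48 does not reproduce as the number needed for 90% power: an exact one-sample two-sided t-test on these inputs needs 32, and 48 gives 98.3%. That is a separate matter and does not bear on this point.

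**Step 3. The estimate from the plan as written.** Complete pairs, n = 48:

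12 ± t(47) × 20/√48 = 12 ± 5.81, that is 6.2 to 17.8, p = 0.00014.

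**Step 4. What imputation would do if someone forced it.** Both methods below are assumptions; the SAP names neither.

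*Zero change for all 12 missing subjects.*
- Mean = 48 × 12 / 60 = 9.6.
- Sum of squares = 47 × 400 + 48 × (12 − 9.6)² + 12 × 9.6² = 18,800 + 276.5 + 1,105.9 = 20,182.4.
- SD = √(20,182.4 / 59) = 18.50.
- 95% CI 4.8 to 14.4, p = 0.00017.

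*Observed mean for all 12.*
- Mean 12.0; SD = √(18,800 / 59) = 17.85.
- Half-width 4.61, so 95% CI 7.4 to 16.6.
- The interval is 1 − 4.61/5.81 = 21% narrower with no new data. Under no true change the two-sided error rate would be 11.7% instead of 5%.

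*Fewer missing, 60 enrolled, zero change:* mean = 12 × (60 − k)/60, which is 11.4 at k = 3 and 10.8 at k = 6.

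The largest shift in the mean is 12.0 − 9.6 = 2.4 points, at k = 12. Reaching it means imputing for the whole planned loss, including early leavers with no V12 assessment, whom SAP 6.2 excludes.

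**The case for a change.** The best case for a change is that the text does say results will be imputed, and that the harmless reading has to be inferred. The SAP never says whether an imputed score could make a subject Evaluable, and 16.2.1 makes no exception for subjects who have left. With only one visible post-baseline time point for the primary score, reading the clause as covering gaps during the study seems to leave it nothing to do. Deleting it would cost one sentence.

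Part of this stands. The clause is loosely drafted, sits under the wrong heading, and gives no method. The rest does not carry through to a result.

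- SAP 6.2 asks for an assessment the subject has had. A filled-in value is not an assessment, and nothing in either document suggests that it counts as one.
- 16.2 is the specific rule for subjects who have left, and a specific rule ordinarily governs over a general sentence in a subsection on dates.
- That the clause has no work to do during the study cannot be established. Protocol Table 6.1 and the body of 6.2 are not shown, and parts of SAP 10 are redacted. If scores are collected at interim visits, the clause has an ordinary target that does not enter the primary test.
- The worry about N is slight. Protocol 11.1 defines n as the number of observations, and the SAP 10 table lists statistics of changes, so a count of change scores is the natural reading.

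**Conclusion.** No change to the plan is needed. The wording of 16.2.1 is at odds with 16.2, but the conflict does not reach the primary estimate. Subjects who meet the clause's condition are outside the Evaluable Population, and Evaluable subjects with a blank FACE-Q are outside the clause. An analyst who follows the plan reports the complete-pair result, on planning inputs 12.0 (6.2 to 17.8) from 48 subjects, which is also what an explicit no-imputation rule would give. Removing the clause would tidy the text without altering any number.

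The 0 to 2.4 point range and the 21% narrowing are effects of imputation methods assumed here, not of the SAP, and p stays below 0.001 throughout. The conclusion rests on two readings: that an imputed value does not make a subject Evaluable, and that exit data map to V12. The first follows from the definition in SAP 6.2; the second is supported by protocol 11.1 and the contents entry for 6.2.3.4.

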16.3 Missing Severity Assessment for Adverse Events

If severity is missing for an AE that started before the date of the first dose of study treatment, an intensity of mild will be assigned. If severity is missing for an AE that started on or after the date of the first dose of study treatment, an intensity of severe will be assigned. The imputed values for severity assessment will be used for the incidence summary; the values will be shown as missing in the data listings.

17 DATA COLLECTED BUT NOT ANALYZED

This section is not applicable to this study.

18 CHANGES TO ANALYSES SPECIFIED IN PROTOCOL

Change to analyses specified in protocol is not applicable to this study.

